#### **N. Drug supplies**

The study intervention, triamcinolone acetonide (Kenalog® for injection), is FDA-approved for the treatment of asthma in children. There is no IND associated with this study. The drug will be administered consistent with the instructions listed in the accompanying package insert.

The following drug supplies will be provided by the research pharmacy:

- Triamcinolone acetonide (Kenalog® for injection), 1 mg/kg, 40 mg max
- Albuterol sulfate (90 mcg/inhalation) for bronchodilator reversibility testing and sputum induction
- 3% saline for sputum induction (substitutions and compounding permitted)

#### **O. Study failure**

Given the observational nature of this study, there are no specified criteria for study failure. Communication with each participant's primary caregiver will be ongoing.

#### **P. Availability of study personnel**

The study physician ([name]) will be available for discussion with families 24 hours/day should uncertainty or questions arise regarding the study. Communication regarding the study, receipt of triamcinolone, and laboratory results will be sent to the child's primary care provider. At all study visits, coordinators will emphasize the importance of maintaining contact with the child's primary care provider.

## **Q. Recruitment and Retention**

Prospective enrollees will be enrolled at Children's Healthcare of Atlanta, which serves an urban population with diverse demographic features including race, ethnicity and socioeconomic status. Eligible participants will be identified from within the Children's Healthcare of Atlanta system by ICD-10 codes for wheezing and asthma. We will obtain a HIPAA waiver from the Emory and Children's Healthcare of Atlanta IRBs for this purpose (i.e., identification of eligible participants). Once the list of eligible participants is generated, IRB-approved mailings will be sent to these families informing them of the study and the phone number/email address of the study coordinator to use if they would like more information. We will also run printed advertisements in Atlanta Parent Magazine and contact previous study patients/caregivers (who have given us permission to do so) to see if they are interested. We anticipate no problems with our recruitment approach since the burden of asthma and wheezing disorders is significantly higher in Georgia versus other states. Indeed, the current asthma prevalence in children in Georgia is 12.1% compared to a pooled estimate of 9.0% in 38 other states. Our planned recruitment strategies were also previously utilized in our NHLBI AsthmaNet studies and yielded a large number of eligible participants who were interested in research. Emory University, under the leadership of [name], was one of the lead recruitment sites for multiple NHLBI longitudinal asthma studies.

Retention of research participants is essential for this longitudinal study. In our experience, the best retention method for participants in long-term clinical studies is education and continual "reminders." For all participants enrolled in our clinical research studies, including the study proposed here, newsletters are distributed every 3 months (by mail or email) that include educational material about respiratory health, bulletins of important issues that affect patients (flu vaccines), and study updates. We also have several additional methods to encourage continued involvement in our studies, including distribution of materials with our logos and contact numbers and other continual "reminders" of study involvement (refrigerator magnets, pens, mugs, t-shirts or blankets). Other retention efforts will focus on ease of the majority of visits and informational rewards (such as asthma education). Visits will be at times convenient to the parents, many of whom are employed. Appointments after school will also be available. Study team members will be available to answer questions about asthma. The study physician will also be available by phone during off-hours to aid in the management of adverse events including asthma exacerbations.

Participants will also be paid for their time and participation in the study. While we will enroll 173 children, we expect some dropout to occur. Study visits will be pro-rated accordingly, and families will be paid at the end of each visit. Parking passes are also provided so that families do not have to pay for parking. In the event that transportation is a challenge, we also pay for taxis to pick up participants at their homes and drive them to the study site.

## R. Risks and benefits

**Asthma exacerbation.** The inclusion criteria require that all participants have a history of asthma exacerbation, and therefore we can expect a similar pattern of illness (i.e., a high probability of subsequent exacerbation) in the year of study enrollment. While we do not anticipate that children enrolled in this study will have significant worsening of asthma symptoms as a result of the study procedures, children enrolled in this trial may develop an asthma exacerbation of sufficient severity to warrant emergency medical care. Hospitalization will be considered a Serious Adverse Event, and be reported to local IRBs in the usual manner.

**Parent-completed questionnaires (medical history, demographics) and child-completed questionnaires (asthma control, PROMIS symptoms).** Participants will complete a variety of questionnaires at each study visit. There are minimal risks to answering these questionnaires, although they may be considered long with repeating questions. For certain questions (such as those that ascertain family education or income level), participants will be allowed to decline from responding. Some of the questionnaires pertaining to depression and anxiety may also highlight significant yet undiagnosed mental health disorders. We will encourage all children to discuss their concerns with their parents, teachers or physicians. In more severe cases, we will also identify available support services through Children's Healthcare of Atlanta and share these with participating children and their families. In severe cases where suicidal ideation is stated or presumed, emergency referrals will be made in accordance with Children's Healthcare of Atlanta policies and procedures.

There is a rare risk that information from a study can be disseminated in ways that can risk the privacy of a person with attendant social and occupational harm. However, this risk is not as great for conditions like asthma, which are common. Regardless, care will be taken to ensure confidentiality. Research records will be held in locked cabinets or secure storage rooms. All transmission of data to the study co-investigators for analysis is by study ID code only. Publication of results will involve aggregate data only so that individual participants cannot be identified. On occasion it may be necessary, for legal reasons or for good clinical practice, for third parties such as the FDA, IRB, or NIH to review medical records that are identified by name. However, this is not a common occurrence, and every effort will be made by the investigators to provide confidentiality for such audits.

**Urine pregnancy testing.** Women of child-bearing potential will submit a urine sample at each study visit for pregnancy testing. Pregnancy is an exclusion since intramuscular triamcinolone acetonide is classified as category C for pregnant women and may be associated with virilizing effects on the human fetus. In the event that a female participant becomes pregnant during this study, she will be withdrawn immediately and referred to her primary physician for further treatment. The perinatal outcomes of any pregnancies will be reported. This will be considered an adverse event and will be reported to the local IRB. The ascertainment of sexual activity, use of birth control, and administration of pregnancy tests to girls age 11 and older is a sensitive issue. In the NHLBI's Childhood Asthma Management Program (CAMP), parents were informed in the initial consent process that the study

coordinators or physicians may ask the participants confidential questions about their health or administer pregnancy tests. Our medical team and research staff are versed in the sensitive acquisition of this information from adolescents and exchange experiences and effective communication techniques. Whether a pregnancy needs to be reported to the participant's parent (legal guardian) is a matter of local hospital policy and state law that will not be addressed as a separate study policy, but we strongly advocate the practice of informing participant's parents with the consent of the participant and referral for appropriate prenatal care.

**Spirometry with Oscillometry.** Participants will undergo spirometry with oscillometry (lung function tests) at each study visit. These tests can cause children to become light-headed or dizzy. The risk of syncope is minimized by having participants sit during the procedure. These tests may also result in shortness of breath or cough. Treatment (albuterol sulfate) will be available if these symptoms occur. However, in the Childhood Asthma Management Program, in approximately 12,000 spirometry tests in children age 6-15 years, there were no serious adverse events.

**Bronchodilator reversibility testing.** Children will undergo spirometry with bronchodilator reversibility testing at visits 1, 2 and 5. This involves administration of 4 inhalations of albuterol sulfate through a metered dose inhaler with a mouthpiece. Side effects of albuterol administration may include nervousness, hyperactivity, increased heart rate, nausea, or headache. These side effects are temporary and should resolve within 15 to 30 minutes.

**Exhaled nitric oxide determination.** Exhaled nitric oxide testing will be performed at each study visit. Exhaled nitric oxide testing can cause similar risks as spirometry but these risks are less intense and are even more rare. Exhaled nitric oxide tests involve breathing into a device at a flow rate that is held constant by an in-line resistance valve. As a result, participants occasionally perceive an inability to freely exhale, or similar to spirometry, may complain of light-headedness.

**Venipuncture.** Blood will be collected by venipuncture for the following: 1) total and allergen-specific IgE, 2) complete blood count with differential, 3) cytokine analyses, and 4) metabolomic analyses. The blood draw will involve a maximum of 12 mL (about a tablespoon) and this volume is well below our local IRB guidelines of no more than 1 mL/kg. Therefore, the risk of anemia is extremely small. This blood will be collected with a butterfly needle and aliquoted into the necessary tubes to avoid participant burden related to multiple needle insertions. A maximum of three attempts will be made to obtain the blood sample. The volume of blood is not expected to be an issue. To minimize risk to the participants, fasting will not be required. Risks of venipuncture can include brief pain during the needle insertion, local bruising at the collection site, and small hematomas. Rarely, children can get light-headed or even faint. Venipuncture can also cause anxiety in children. Therefore all pediatric venipunctures will only be performed by pediatric phlebotomists who are trained in pediatric blood collection methods, which differ from those in adults by the use of topical anesthetic creams and small gauge

needles. In our experience from several local and multi-center pediatric asthma studies which involve blood draws, the most effective strategy for dealing with children is honest explanation of the procedure and associated feelings/sensations (such as “pressure, prick, pinch”), how long those sensations last, strategies to overcome those sensations (singing, thinking about “happy” thoughts), and other coping strategies.

**Sputum induction.** Sputum induction will be performed in participants 12-21 years of age at visits 1, 2 and 5 for cytokine and metabolomic assays. Induced sputum can lead to increased wheezing, coughing and dyspnea and thus, sputum induction will be halted if participants become increasingly symptomatic or do not tolerate the procedure. Our manual of procedures includes frequent measurements of peak expiratory flow to prevent excessive bronchospasm during sputum induction and the safety of this procedure in moderate-severe obstructive lung disease (asthma) has been published. Additionally, the following safety procedures will be followed: 1) a physician will be available during the procedure, 2) all participants will be pre-treated with 4 inhalations of albuterol before the procedure, and 3) only participants with a post-bronchodilator forced expiratory volume in one second (**FEV1**) of >70% predicted will undergo the procedure. Spontaneous sputum samples may be collected on children with an FEV1 below these limits. Study staff will calculate and record the peak flow and FEV1 value that equal both a 10% and 20% fall in lung function based upon the recorded post-bronchodilator peak flow and FEV1 values. Children will not be discharged until FEV1 is within 10% of their post bronchodilator FEV1.

**Triamcinolone injection.** Triamcinolone acetonide injectable suspension (Kenalog®, 40 mg/mL) provides a synthetic corticosteroid with anti-inflammatory action. Triamcinolone acetonide is FDA-approved and indicated for children 6 years of age and older with asthma. The suggested initial dose for children 6-12 years of age is 40 mg, although dosage depends more on the severity of symptoms than on age or weight. For this protocol, children will receive 1 mg/kg in one intramuscular dose (up to 40 mg maximum). Although local side effects of intramuscular administration have been reported, including pigmentation changes and subcutaneous and cutaneous atrophy, these side effects are minimized by deep injection into the gluteal muscle. All triamcinolone acetonide injections will be administered by an experienced pediatric registered nurse. Systemic side effects with a single triamcinolone acetonide injection (40 mg max) are rare and triamcinolone acetonide injection is thought to be generally safe in children. Recent studies of much higher doses of intramuscular triamcinolone acetonide in children with nephrotic syndrome (~2 mg/kg) and difficult-to-treat asthma (60 mg) have revealed little side effects and good tolerance of the medication, with no reported incidence of cataracts, diabetes, added weight gain, or arterial hypertension. Although repeated use of triamcinolone was associated with slightly decreased growth velocity during the active treatment phase (2 mg/kg injection each month for up to 36 months), growth velocity returned to normal after discontinuation of triamcinolone therapy. Nonetheless, participating children will be screened thoroughly by the study physician for the presence of any co-morbid conditions that may increase the risk of triamcinolone acetonide administration. Children receiving triamcinolone acetonide will be educated about signs of potential complications and will have

24-hour access to an on-call pediatric physician. Participants will also undergo a comprehensive evaluation 2 weeks after the triamcinolone acetonide is administered.

Triamcinolone acetonide is a pregnancy category C medication and will not be administered to pregnant adolescents due to potential virilizing effects on the fetus.

Children receiving triamcinolone acetonide injection can experience localized pain at the injection site. This risk will be minimized through the application of topical ethyl chloride anesthetic prior to injection.

**Potential benefits.** While some study participants may receive no direct benefit from participating in this study, others may benefit from the close monitoring of their respiratory health, specialized asthma education, and general evaluation of their condition, including aeroallergen sensitization profiles. Some families also achieve psychological benefit from participating in an important research study and from interaction with the study staff. There is a possibility that the knowledge obtained from participation in this study (i.e., allergen sensitization profiles, lung function results, symptom profiles and corticosteroid treatment responsiveness) will directly benefit the majority of the participating children and their families.

All research procedures will be completed free of charge to the research participants and their families. All research data will also be shared with the caregivers (or the legal guardians). Data that may influence the clinical care of the participant, such as allergen sensitization reports and complete blood counts, will also be shared with the participant's primary care physician. Every child enrolled in this research protocol will also undergo a medical respiratory evaluation at several time points and the information obtained from this study may be useful in the development of specialized respiratory care. It is also possible that the knowledge obtained from this study, such as identification of biomarkers, may assist in the creation of novel asthma therapies in the future.

## **S. Data and Safety Monitoring Plan**

This protocol has a Data and Safety Monitoring Plan that was reviewed and approved by the NIH/NINR and the IRB. This Plan is available as an attachment in the IRB application and will adhere to all aspects of the protocol. The DSMP attachment provides an overall framework for monitoring including :1) Monitoring Entity, 2) Procedures for Monitoring Safety and Minimizing Risk, 3) Data Quality, Management, Confidentiality and Security, 4) Adverse Events and Unanticipated Problems, and 5) Assessment of External Factors or Relevant Information.

## **T. Sample size**

The sample size is 173 participants age 6 up to 21 years, which accounts for a conservative attrition rate of 15% (final N=147). The following assumptions were used for sample size calculations:

- Identification of 4 symptom clusters resulting in 3 degrees of freedom,

- >80% desired power for a chi-square test of multiple proportions,
- Two-tailed significance level of 0.05 if the effect size (W) is small-to-medium by Cohen's convention and equivalent to W=0.275 (small effect: W=0.10, corresponding odds ratio=1.49; medium effect: W=0.30, corresponding odds ratio=3.45), and
- Sample size allocation ratio of 1-2 per cluster group and sample sizes of at least 20 per group.

The sample size calculations with the above parameters should achieve at least 80% power as shown in **Table 3**.

For the secondary outcome, The sample size of 173 children necessary for the primary outcome should achieve >85% power to detect a difference of 0.2 between group means (considered a small effect size  $d$ ) with standard deviation of 0.20. Power >80% is achieved if the mean difference between groups and associated standard deviation is slightly larger but still small (0.25-0.30). In our prior study of triamcinolone administration to children with asthma, mean ( $\pm$  standard deviation) quality of life scores (on a different instrument, the Asthma Quality of Life Questionnaire) were 6.17 ( $\pm$  0.75) and 5.07 ( $\pm$  0.99), respectively. If similar differences are noted between two symptom cluster groups, we should have >90% power for the primary outcome and >95% for the secondary outcome if the groups have at least 20 participants. With smaller group sizes of only 13 participants, power would be >81% and >89% for the primary and secondary outcomes, respectively.

Drop-out	df	Power if effect size is:				
		0.250	0.275	0.300	0.325	0.350
10% (N=156)	3	0.749	0.833	0.897	0.941	0.969
	4	0.703	0.795	0.867	0.920	0.956
	5	0.664	0.760	0.840	0.900	0.942
12.5% (N=151)	3	0.734	0.820	0.886	0.933	0.963
	4	0.687	0.780	0.855	0.911	0.949
	5	0.648	0.744	0.826	0.889	0.934
15% (N=147)	3	0.721	0.808	0.877	0.926	0.959
	4	0.674	0.767	0.844	0.903	0.943
	5	0.634	0.731	0.814	0.878	0.927

**Table 3.** Estimated power.

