## E. Study population

We will enroll a cohort of 173 children age 6 up to 21 years with exacerbation-prone asthma. Participants will be given the option to either: 1) complete a single study visit, with telephone/email contacts and a review of their electronic medical record for up to 48 weeks after enrollment, or 2) complete the 48-week cohort study with scheduled study visits. Participants who select option 2 with follow-up over 48 weeks will also have the option to complete visits 3, 4 and 5 by telephone.

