#### **H. Rationale for triamcinolone acetonide injection**

At the completion of the baseline visit, a subset participants who consented to the 48 week cohort study will receive intramuscular triamcinolone acetonide (Kenalog,® 1 mg/kg, up to 40 mg maximum) administered deep in the gluteal muscle by a trained registered nurse. Corticosteroids are the cornerstone of treatment for asthma; intramuscular triamcinolone was selected as the treatment of choice over oral prednisolone or inhaled corticosteroids to allow for characterization of corticosteroid insensitivity without the confounding effects of poor adherence or inadequate drug delivery or absorption. We further considered the pharmacology of corticosteroids. Because triamcinolone has 20% more glucocorticoid activity than prednisolone, triamcinolone 1 mg/kg will ensure that participating children have a sufficient dose of corticosteroid to achieve the desired potential anti-inflammatory effects. In previous studies of adults, a single dose of 80 mg of triamcinolone significantly improved lung function and asthma symptoms in the majority of patients. Given several previous studies in children and our own published studies of triamcinolone responsiveness in children with asthma, a dose of 1 mg/kg of triamcinolone should elicit a clinical response. Because inclusion is limited to children with a recent exacerbation (many of whom will have poor symptom control and all of whom are at risk for future exacerbation), all participants have the potential to benefit from this procedure. The safety of our dosing strategy has also been well established. In our previous study ([name] R01NR012021), the triamcinolone injection was well tolerated and no unexpected adverse events were reported. Expected adverse events

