## J. Outcome measures

Asthma exacerbations are an outcome of interest for all participants.

For participants enrolled in the 48-week cohort study, the primary outcome is corticosteroid treatment responsiveness, assessed 14 days after systemic triamcinolone administration (at visit 2). Responsiveness will be determined from the mean difference in the Asthma Control Questionnaire (**ACQ**) score between visit 1 (baseline) and visit 2 (14 days), with a reduction of 0.5 considered a minimally important difference.

The secondary outcome for participants enrolled in the 48-week cohort study is quality of life, assessed by the PROMIS Pediatric Asthma Impact Scale (**PAIS**) at visits 3, 4 and 5. As with all PROMIS measures, the PAIS is scored on the T-score metric, with higher scores reflecting more of the concept being measured. On the T-score metric, 50 is the mean of the reference population and 10 is the standard deviation; thus scores of 40 and 60 are one standard deviation lower and higher than the mean of the reference population, respectively.

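### Power for the primary outcome is computed on all 173 enrolled, although children who choose Option 1 cannot have that outcome

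*Combined protocol and SAP*

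**What the plan says.** Section T (Sample size) sets enrolment at 173, "which accounts for a conservative attrition rate of 15% (final N=147"). It assumes "Identification of 4 symptom clusters resulting in 3 degrees of freedom". The target is stated as ">80% desired power for a chi-square test of multiple proportions", the error rate as "Two-tailed significance level of 0.05", and the effect size as "equivalent to W=0.275". Table 3 gives power for 10%, 12.5% and 15% drop-out only. The text on the secondary outcome describes 173 as the number required for the primary outcome.

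Section E, repeated in Section I, describes who the 173 are: "Participants will be given the option to either: 1) complete a single study visit", with telephone or email contact and record review afterwards, or the 48-week cohort with scheduled visits. Sections I and K list no injection, no visit 2 and no 14-day ACQ under Option 1; its later ACQ contacts are at 24 and 48 weeks.

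Section J restricts the endpoint: "For participants enrolled in the 48-week cohort study, the primary outcome is corticosteroid treatment responsiveness", measured at visit 2, 14 days after the injection. Section H adds that "a subset participants who consented to the 48 week cohort study will receive intramuscular triamcinolone acetonide". Section U compares the proportion with an ACQ improvement of at least 0.5 across latent classes by chi-square.

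No section gives a target, a minimum or an expected share for Option 2. Section B still describes a 48-week cohort with N=173.

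**The concern.** A child who chooses Option 1 has not dropped out. By design that child has no response to triamcinolone to measure, yet is counted in the N behind the primary power figure. The single-visit option came in with Version 4, according to the summary of changes, and the current Section T makes no allowance for it.

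The N that matters is the number of Option 2 children with an ACQ at visits 1 and 2. If it is well below 147, the test of whether symptom clusters differ in corticosteroid response is underpowered for the effect the plan names, and a null result could be read as coming from an adequately powered study. The secondary outcome, PAIS at visits 3, 4 and 5, is also defined for Option 2 only, while its power statement also uses 173.

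**Working it through.** **Inputs.** From Section T: 173 enrolled, 15% attrition, df = 3, alpha = 0.05, W = 0.275, target power above 80%, at least 20 children per cluster. From Sections E, I and J: the 173 cover both options, and only Option 2 has the primary outcome. The Option 1 share, *p*, is not in the documents; it is an assumption and is shown as a range.

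**Formula.** Power = 1 − F(c; df, λ), where F is the noncentral chi-square distribution function, λ = N × W², and c = 7.815 is the 95th percentile of the central chi-square with 3 df.

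**Step 1: reproduce the plan.** 173 × 0.85 = 147.05, so N = 147. λ = 147 × 0.275² = 11.117, giving power 0.808, as in Table 3. All 45 cells of Table 3 reproduce within about 0.001, so the method is the plan's own and its arithmetic is correct.

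**Step 2: minimum N.** At W = 0.275, N = 145 gives 0.8025 and N = 144 gives 0.7995. The minimum is 145, so 147 leaves a margin of two children.

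**Step 3: room for Option 1.**
- With 15% attrition: 145 / 0.85 = 170.6, and 173 − 170.6 = 2.4. Two Option 1 children leave 171 × 0.85 = 145.4; three leave 170 × 0.85 = 144.5, below 145.
- With no attrition: 173 − 145 = 28, and 28 / 173 = 16%. This is the most that Option 1 choice and every other loss before visit 2 can total.

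**Step 4: power over a range of uptake.** Evaluable N = 173 × (1 − *p*) × 0.85. The last column drops the attrition factor.

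| Assumed Option 1 share | Evaluable N (15% attrition) | Power at W=0.275 | W detectable at 80% power | Power with no attrition |
|---|---|---|---|---|
| 0% | 147 | 0.81 | 0.272 | 0.87 |
| 5% | 140 | 0.79 | 0.279 | 0.85 |
| 10% | 132 | 0.76 | 0.287 | 0.83 |
| 20% | 118 | 0.71 | 0.304 | 0.78 |
| 30% | 103 | 0.64 | 0.325 | 0.72 |
| 50% | 74 | 0.49 | 0.385 | 0.56 |

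**Step 5: cluster size.** At a 50% share, 73.5 / 4 is about 18 children per cluster on average, below Section T's own minimum of 20.

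**Step 6: enrolment that keeps the stated power.** 173 children are needed in Option 2 alone, so total enrolment is 173 / (1 − *p*): 193 at 10%, 231 at 25%, 346 at 50%.

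**The case against.** The strongest reply is that the loss is conditional. Uptake of Option 1 is not stated, so no particular power can be called the true one, and low uptake does little harm: at 5% the power is 0.79 against 0.81. That stands, and it is why the results are given as a range.

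A second reply is that 15% is a conservative figure for a 48-week study, whereas the primary outcome is read at 14 days. If only 5% were lost by then (an assumption), a 10% Option 1 share would leave 173 × 0.90 × 0.95 = 148 children and power of 0.81. This is fair, and the no-attrition bound of 28 children does not depend on when losses occur. But Table 3 itself applies the 15% to the primary test, and nowhere does the plan say that this allowance is meant to absorb Option 1.

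Third, at W = 0.30, another column of Table 3, power at a 10% share with 15% attrition is still 0.84. True, but the sample size is justified at W = 0.275.

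Fourth, Section B can be read as meaning 173 in the 48-week cohort, with Sections E and I loosely worded. Those two sections say plainly that the 173 choose between options, so the passages conflict, and a correction is needed under either reading.

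Finally, Section U includes all participants in the latent transition analysis, and Option 1 children give ACQ and asthma-impact scores at 24 and 48 weeks. Neither supplies a change in ACQ at visit 2, and Section J does not count the later contacts towards the secondary outcome.

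**Conclusion.** The concern holds. The calculation in Section T is numerically right but uses a population that includes children who cannot contribute the primary outcome. Its claim of at least 80% power at W = 0.275 survives only if no more than 2 of 173 choose Option 1 (15% attrition) or no more than 28 (no attrition). At assumed uptake of 10% to 50% with the plan's attrition, power is 76% down to 49%, and the detectable W rises from 0.272 to between 0.287 and 0.385. The size of the shortfall depends on the uptake, which the documents do not give; the mismatch between enrolment and analysis population does not.

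If the wording in Section H means that only some Option 2 children are injected, the evaluable number is smaller still. Section L says that every participant meeting the criteria receives the injection, so these two passages must be reconciled.

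**What to change.** This must be corrected before the power statement is relied on.

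- Restate Section T and Table 3 for the number of Option 2 participants expected to have an ACQ at visit 1 and visit 2. Give power and detectable W for that number over a stated range of Option 1 uptake, or at the observed uptake if it is known.
- State that 173 is total enrolment, serving baseline clustering and exacerbations, and correct the N given for the 48-week cohort in Section B. If 173 is instead meant as the Option 2 target, say so in Section T and amend Sections E and I so that Option 1 is enrolled in addition.
- Restate the secondary-outcome power on the Option 2 number as well.
- Reconcile Sections H and L on who receives the injection.

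Restating costs protocol and SAP wording and a recalculated table, with no extra participants, but the stated power becomes less favourable. Keeping the target of more than 80% at W = 0.275 would require the larger enrolment in step 6 of the working.
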